3.1. Intended use

Current indication for use of the device:

The Nerivio[™] is indicated for acute treatment of migraine with or without aura in patients 12 years of age or older. It is a prescription use, self-administered device for use in the home environment at the onset of migraine headache or aura.

This study aims to evaluate the effect of the Nerivio treatment in subjects with New Daily Persistent Headache (NDPH) in adolescents (12-17 years of age).

3.2. Device description

The device is a wireless wearable battery-operated stimulation unit controlled by a dedicated smartphone application. Treatments with NerivioTM are self-administered by the user at the onset of a headache.

The Nerivio[™] (Figure 1) includes several main components:

- A pair of electrodes covered with hydrogel and a removeable protective film
- An electronic circuitry and a battery
- A software that includes firmware and a software application for mobile platforms
- An armband to secure the attachment of the device and enable a discreet treatment

Revision #: 1.0

Page: 10 of 20

[figure not shown]

Figure 1 - Nerivio™ device. (A) Internal side, (B) External side, and (C) The armband

3.3. The application

Activation, control over stimulation intensity and termination of stimulation are performed via a dedicated smartphone application and installed on the user's cell phone. The application has a graphical user interface (GUI)γ

The Nerivio application also includes a "headache diary" which collects information on the headache and the treatment (e.g. date & time, location, headache pain intensity, etc.). The application also provides notifications and indications on connection state and remaining number of treatments.

The application can be installed from Google Play or the App store and supports Hebrew and English menu displays.

Revision #: 1.0

Page: 10 of 20

Figure 2: The app main screens

4. Objectives & hypotheses

4.1. Study objectives

The objective of this study is to evaluate the safety and efficacy of Nerivio[™] for the acute treatment of NDPH in adolescents. The goal of this study is to demonstrate headache relief without unexpected device-related adverse effects.

4.2. Study hypothesis

The hypothesis of this study is that in adolescents, REN with Nerivio[™] will provide clinically meaningful relief of NDPH pain with a favorable safety profile.

5. Study design

5.1. Participants

This study will be conducted on up to 100 eligible participants.

5.1.1. Inclusion criteria

- Participants age 12-17 years old at the time of informed consent, inclusive.
- Participants have at least a 6-month history of headaches that meet the diagnostic criteria for New Daily Persistent Headache (NDPH)
- Participants who are on stable dosing of prophylaxis agents for at least three months.
- Participants have personal access to a smartphone (24/7)
- Participants must be able and willing to comply with the protocol
- Parents/Guardians must be able and willing to provide written informed consent
- Participants must be able and willing to provide informed assent

5.1.2. Exclusion criteria

- Participants with an implanted electrical and/or neurostimulator device (e.g. cardiac pacemaker, cochlear implant).
- Participants with congestive heart failure (CHF), severe cardiac or cerebrovascular disease.
- Participants with epilepsy.
- Participants who have undergone nerve block (occipital or other) in the head or neck, or treatment with onabotulinum toxin A (Botox) to the head and/or neck in the prior four months.
- Current participation in any other clinical study that includes treatment

Revision #: 1.0

Page: 11 of 20

- Participants without basic cognitive and motor skills required for operating a smartphone.
- Pregnant or breastfeeding females
- Participants who have previous experience with the device
- Participants with arm circumference below 7.9 inches (20 cm)
- Patient has, in the judgement of the investigator, a psychiatric disorder as defined by the *Diagnostic and Statistical Manual of Mental Disorders, 5th Edition*, that would interfere with adherence to study requirements or safe participation in the trial. This includes a current or historical diagnosis of a substance use disorder.
- Patient is, in the judgment of the investigator, actively suicidal and therefore deemed to be at significant risk for suicide.
- At Screening patient has answered "yes" to either Question 4 or Question 5 on the "Suicidal Ideation" portion of the Columbia-Suicide Severity Rating Scale (C-SSRS) or has answered "yes" to any of the suicide-related behaviors on the "suicidal behavior" portion of the C-SSRS, and the ideation or behavior occurred within the past month. If reports of suicidal ideation with intent to act (endorse item 4 or 5), reports of actual, aborted, or interrupted suicide attempts, or reports of behavior preparatory for an attempt are identified, the investigator is to appropriately manage the subject in accordance with standard of care.

5.1.3. Withdrawal/discontinuation

Participants may withdraw consent at any time without and do not have to provide an explanation.

Participant may be withdrawn from the study by the PI due to one or more of the following reasons:

- Participant is lost to follow-up
- Refusal of the participant to continue treatment and/or follow-up observations
- · Serious adverse event
- Participants encountering difficulties with the investigational product (IP) (e.g. cannot tolerate the treatment, unable to operate the application)

Revision #: 1.0

Page: 12 of 20

- Significant protocol deviation/violation or noncompliance, either by the patient or the investigator
- Decision made by the investigator that termination is in the patient's best medical interest
- Device malfunction
- Other ethical or clinical considerations upon investigator discretion

5.2. Procedures

This open label study includes 2 phases and up to 3 visits. All visits will be conducted in the presence of a parent/guardian.

First visit - enrollment: The first visit will include screening, enrollment and training on operating the headache diary within the smartphone application. The screening process will include an eligibility assessment and a urine pregnancy test (if required). Following successful screening, enrollment interview and signing an informed consent by the parent/quardian and an informed assent by the participant. The participants will be trained to use the electronic diary application, installed on their own smartphones. During this visit, participants will complete baseline questionnaires that included information on the headaches (frequency, severity, etc...), typical associated symptoms, use of preventive and abortive medications/treatments, and the effect that their headaches on their daily routine and quality of lifeThe C-SSRS will be administered at the screening visit and a "since last visit" form which will be administered at each subsequent inclinic study visit to assess possible suicidal ideation and behavior. The C-SSRS will be scored by the investigator or Study Coordinator who has C- SSRS certification. The survey will be scored immediately after taken by participant. If reports of suicidal ideation with intent to act (endorse item 4 or 5), reports of actual, aborted, or interrupted suicide attempts, or reports of behavior preparatory for an attempt are identified, the investigator" will refer the subject for further examination.

Phase 1 – run-in phase: After the enrollment visit, participants will undergo a 4-week diary phase aimed to collect baseline NDPH characteristics. Participants will be asked to report in the application each headache attack. These reports will be collected and analyzed.

Second visit – Device training visit: During this visit, participants and their parent/guardian will be trained to use the device, including finding the optimal individual stimulation intensity level (perceptible but not painful).

Participants will be asked to treat their NDPH with the device using the identified optimal intensity. If the research staff recognizes that the participant cannot tolerate the feeling of the electrical stimulation, the participant may be withdrawn from the study.

During the training, participants will also be informed on the key elements which are critical for the successful conduct of the study:

Revision #: 1.0 Page: 13 of 20

- Treatments of headache with Nerivio[™] should be performed within 60 minutes of awakening with a headache or upon increasing headache severity and always within one hour of symptoms onset. Treatments of mild headaches are accepted.
- Avoid taking rescue medications within two hours post-treatment (2 hours from start of treatment), if possible.

Revision #: 1.0

Page: 14 of 20

• The treatment should be performed for 45 minutes.

In addition, participants will complete study questionnaires, as required.

Phase 2 – Treatment phase: Participants will be instructed to use the device within 60 minutes of awakening with a headache or upon increasing headache severity during a period of 4 week. Participants will be instructed to use the device with the intensity level identified during the device training visit (with a range of ±5 units) and make sure the stimulation is perceptible but not painful. Participants will be instructed to avoid taking rescue medications within 2 hours post-treatment. If medications are used, participants will be instructed to record in the app when and which medication was taken. The participants will use the app to record pain intensity levels (none, mild, moderate, or severe) at baseline and 2 hours post-treatment, and to record the presence/absence of associated symptoms (nausea, photophobia, phonophobia) at baseline and 2 hours post-treatment.

Participants who do not achieve satisfactory relief at 2 hours post-treatment may treat again with the Nerivio[™] device or may treat with usual care at that time or any time thereafter if the headache does not resolve.

Third (final) visit – End of study: Participants will return to the clinic following the end of the 4-week treatment phase, at which time they will return the device and complete the required questionnaires

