	3. Participants with epilepsy.4. Participants who have undergone nerve block (occipital or other) in the	
	head or neck, or treatment with onabotulinum toxin A (Botox) to the head	
	and/or neck in the prior four months.	
	5. Current participation in any other clinical interventional study	
	Participants without basic cognitive and motor skills required for operating a smartphone.	
	7. Pregnant or breastfeeding females	
	8. Participants who have previous experience with the device	
	9. Participants with arm circumference below 7.9 inches (20 cm)	
Study Design	A prospective, single arm, open label trial.	
	The study will be conducted in two phases:	

Revision #: 1.0

Page: 6 of 20

	Phase I - Run-in: Eligible participants will use a smartphone headache diary application for 28 days. Participants who report at least 22 entries (70%) AND a constant and unremitting headache will be included in the treatment phase. The C-SSRS will be administered at the screening visit and a "since last visit" form which will be administered at each subsequent in-clinic study visit to assess possible suicidal ideation and behavior. The C-SSRS will be scored by the investigator or Study Coordinator who has C-SSRS certification. The survey will be scored immediately after taken by participant. If reports of suicidal ideation with intent to act (endorse item 4 or 5), reports of actual, aborted, or interrupted suicide attempts, or reports of behavior preparatory for an attempt are identified, the investigator" will refer the subject for further examination. Phase II - Treatment phase: Participants who meet the run-in requirements will receive an active Nerivio device. Participants will be instructed to use the device within 60 minutes of awakening with a headache or upon increasing headache severityduring a period of 4 week. A treatment session is of 45 minutes The participants will use the app to record pain intensity levels at baseline and 2-hours post-treatment, and to record the presence/absence of associated	
Qualifying NDHP attack	A qualifying NDPH attack is defined as a headache that: 1. is at an intensity above their baseline pain 2. is present upon awakening	
Primary endpoint	Pain relief at 2 hours post-treatment: The proportion of participants achieving pain relief at 2 hours post-treatment in the test treatment, with no use of rescue/abortive medication (Pain relief defined as a reduction from severe to moderate, mild or none, moderate to mild or none, or mild to none)	

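### Section 5.2 holds every visit in a parent's presence with no exception for the C-SSRS, so adolescents may under-report suicidal ideation or behaviour

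*Combined protocol and SAP*

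**What the plan says.** Section 5.2 sets the visit structure: "This open label study includes 2 phases and up to 3 visits". The next sentence sets the condition under which they take place: "All visits will be conducted in the presence of a parent/guardian". No exception follows, there or elsewhere.

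On suicidality, the synopsis and section 5.2 both state that "The C-SSRS will be administered at the screening visit", with a follow-up form at each subsequent clinic visit. Scoring is done by the investigator or a coordinator with C-SSRS certification. The respondent is the adolescent: "The survey will be scored immediately after taken by participant".

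The answers are used in two ways. Section 5.1.2 excludes a patient who, at screening, answers yes to ideation question 4 or 5 or to any behaviour item, where this occurred within the past month. The synopsis and section 5.2 require referral if such ideation, an attempt or preparatory behaviour is reported. Section 5.1.2 separately excludes a patient whom the investigator judges to be "actively suicidal and therefore deemed to be at significant risk for suicide".

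Section 11 deals with confidentiality in reports and publications and with national privacy law. It does not say what a parent may hear during a visit.

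**The concern.** A questionnaire on suicidal thoughts and past attempts works only if the respondent is willing to answer candidly. A minor who answers in front of a parent has an understandable reason to hold back. On the C-SSRS the expected direction is towards a true positive being recorded as negative.

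Two things are at stake. At screening, a participant who meets the C-SSRS exclusion could be enrolled. On study, new ideation or behaviour could go unreported, so the referral rule would not be triggered. Little else in the protocol would pick this up: the C-SSRS is the only structured suicidality measure described, and the synopsis says that safety assessment includes adverse events that are spontaneously reported.

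**Working it through.** The plan gives no figure to reproduce, so the check is a comparison of provisions.

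1. **Which visits require a parent?** All of them, up to three (section 5.2).

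2. **At which visits is the C-SSRS given?** At screening, which is part of the first visit, and at each later clinic visit, which means device training and end of study (section 5.2). No administration is described outside a visit, so every one falls under the parental-presence sentence.

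3. **Whose answers are recorded?** The participant's (section 5.2), aged 12 to 17 (section 5.1.1).

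4. **What depends on those answers?** One exclusion criterion turns directly on a yes answer (section 5.1.2). The referral rule turns on what is reported (synopsis and section 5.2).

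5. **Is private administration provided for anywhere?** Not in section 5.2, the exclusion criteria, the consent section (9) or the confidentiality section (11). The consent and assent forms are not in the review copy, so what they say cannot be checked.

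6. **Can the effect be sized?** The expected number of missed positives would be N × p × (1 − d), where N is the number assessed, p the true proportion positive and d the probability that a positive participant discloses. The effect of parental presence would be N × p × (d alone − d with parent). The documents give a planned N of up to 100, but no value for p or for either d. Any result would restate whatever fall in disclosure was assumed, and an assumption of no fall gives zero. No number is therefore put forward.

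**The case against.** The strongest reply is that the sentence governs the visit and not each questionnaire. A parent could be at the clinic while the participant completes the form out of sight, and nothing expressly forbids that. This reading is possible. It is not the plain one: the text has the visit itself conducted in the parent's presence, and the second visit trains participant and parent together. A coordinator who asked the parent to step out would be relying on something the protocol does not say. The proposed sentence is harmless under the looser reading and corrective under the plain one.

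A second reply is that the investigator's judgement gives another route to exclusion, and that a parent may report history the adolescent omits. Both stand in part. The judgement criterion is separate from the C-SSRS answers, and a parent's account could help eligibility as a whole. Neither makes the participant's own C-SSRS answers more candid, and the protocol describes no separate source of information for the judgement.

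A reader might also extend the point to pregnancy and substance use. The documents do not support that. Pregnancy is screened by a laboratory result, as part of an "eligibility assessment and a urine pregnancy test (if required"), and that result does not depend on disclosure. Substance use enters as a diagnosis within a psychiatric criterion left to the investigator: "This includes a current or historical diagnosis of a substance use disorder". No self-report screen is named. It would therefore be wrong to say that three exclusions rest on the adolescent's answers. Only the C-SSRS criterion does so directly.

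**Conclusion.** The point holds for the C-SSRS. The rule as written applies to every administration, the responses are the adolescent's own, and they feed an exclusion and a referral rule. The risk is under-reporting at screening and on study.

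The conclusion rests on two assumptions: that the sentence is applied as it plainly reads, and that a parent's presence makes some adolescents less willing to disclose. The second is reasonable, but the documents do not test it. The size of the effect is unknown.

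A reader might infer that the C-SSRS will under-detect, or that the reported safety results will look better than they are. Neither can be claimed. The documents contain no detection data. The safety endpoints in section 5.3.4 are adverse event incidence and non-completion because of adverse events, and neither they nor the safety analysis in section 6.4.3 names C-SSRS results. The consequence lies in participant protection: who is enrolled and who is referred. That is enough to justify a change this cheap.

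**What to change.** Replace the parental-presence sentence in section 5.2 with wording to this effect: a parent or guardian accompanies the participant to every visit; the C-SSRS is completed by the participant alone with the certified rater; the parent or guardian then rejoins.

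Confirm that the consent and assent forms say that this part is private and what will be shared with the parent, or add it if they do not.

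The sponsor should also reconcile the two existing statements on a positive answer. Section 5.1.2 has the investigator manage the subject under standard of care, while the synopsis and section 5.2 have the investigator refer the subject for further examination. This review takes no position on which should apply.

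The cost is one protocol edit, possibly a line in the consent and assent forms, and a few minutes per visit with the same staff and instrument. Some parents may ask to stay, so the consent discussion should cover this in advance.

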5.3. Study endpoints

5.3.1. Primary endpoints

1. Pain relief at 2 hours post-treatment:

The proportion of participants achieving pain relief at 2 hours post-treatment in the test treatment, with no use of rescue/abortive medication (Pain relief defined as a reduction in pain scale from severe to moderate, mild, or none)from moderate or severe to mild or none.

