6.3. Analysis sets

Intent to treat analysis set (ITT)

The ITT analysis set includes all patients undergoing the treatment phase.

Modified intend to treat analysis set (mITT)

The mITT analysis set includes all patients undergoing the treatment phase and treat at least one (1) treatment within 60 minutes of headache onset. Subjects with no valid post baseline assessment will not be included in the relevant analysis.

Per-protocol analysis set (PP)

The PP analysis set includes all patients from the mITT analysis set without major protocol deviations. Main protocol instructions include:

- has started within 60 minutes of awakening with headache or increased intensity from baseline
 - was administered for 45 minutes
 - includes data on headache intensity at 2 hours post-treatment
 - rescue medication was not used before or within 2 hours post-treatment

Statistical analysis of the analysis sets

The ITT analysis set will serve as the main set for safety assessments.

The mITT analysis set will serve as the primary set for the efficacy assessment.

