6.4.4. Efficacy analysis

The efficacy endpoints will be assessed on evaluable treatments of qualifying attacks. The first use of the device is considered a training treatment and will not be included in the efficacy analyses. The first treatment of a qualifying attack after the training treatment is considered a test treatment and will be used for all efficacy assessments. If this treatment is not evaluable (i.e., no pain data at 2 hours post-treatment), a subsequent treatment of a qualifying attack with evaluable data will be considered the test treatment.

Use of rescue medication before the 2-hours assessment will be considered a treatment failure for the 2-hours endpoints, and before the 24 hours assessment for the sustained 24-hours endpoints. The percentage of participants achieving each of the efficacy outcomes will be presented in a tabular form along with two-sided 95% exact confidence intervals.

For the associated symptoms outcomes, the observed response proportions and corresponding 95% exact confidence intervals for each associated symptom will be provided. All patients with baseline and 2 hours values will be included in the analyses. A response in each associated symptom (nausea, vomiting, photophobia, phonophobia) is defined as change from presence of a specific associated symptom at baseline to absence of the same associated symptom at 2 hours post-treatment.

In addition, logistic regression models will be used to assess the efficacy. Baseline value and site will serve as covariates.

The first secondary endpoint (pain relief at 2 hours) may also be evaluated in attacks with aura and attacks without aura separately.

7. Data management

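### Rescue use, a component of the primary endpoint, is captured only by a conditional app entry, so no use and unrecorded use cannot be told apart

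*Combined protocol and SAP*

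**What the plan says.** Section 5.3.1 defines the primary endpoint in two parts: "The proportion of participants achieving pain relief at 2 hours post-treatment in the test treatment, with no use of rescue/abortive medication". The functional-disability endpoint in 5.3.2 carries the same no-rescue condition, and the consistency endpoint there inherits the primary definition.

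Section 5.2 describes how each part is collected in the treatment phase. Pain grade is entered at baseline and at 2 hours. Participants are also asked "to record the presence/absence of associated symptoms (nausea, photophobia, phonophobia) at baseline and 2 hours post-treatment". For rescue, the wording is conditional: "If medications are used, participants will be instructed to record in the app when and which medication was taken". The training instruction is "Avoid taking rescue medications within two hours post-treatment (2 hours from start of treatment), if possible".

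Section 6.4.4 gives the analysis rule: "Use of rescue medication before the 2-hours assessment will be considered a treatment failure for the 2-hours endpoints". It moves to a later treatment only under this condition: "If this treatment is not evaluable (i.e., no pain data at 2 hours post-treatment". It gives no rule for a treatment whose rescue status is unknown. Section 6.3 adds that "The mITT analysis set will serve as the primary set for the efficacy assessment", and its per-protocol criteria exclude rescue taken before the treatment or in the 2 hours after it.

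**The concern.** Pain and symptoms each produce a recorded value whichever way the answer goes. Rescue produces a record only when it is taken and entered. The absence of a record is then the only evidence for the no-rescue half of the primary endpoint, and that absence has two possible causes.

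If some participants take a drug, improve and make no entry, the analysis credits the device with a response that the endpoint definition counts as a failure. The study is single arm, so there is no comparison group in which the same error could cancel. Rescue within 2 hours is foreseeable: the instruction to avoid it is qualified, and 6.4.4 has a failure rule for it.

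**Working it through.** **Step 1. How the rules treat each case.** Apply 5.3.1 and 6.4.4 to a test treatment with a 2-hour pain score on which rescue was taken before 2 hours.

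| Pain grade lower at 2 h | Rescue entered | Status by definition | Status as analysed |
|---|---|---|---|
| Yes | Yes | Failure | Failure |
| Yes | No | Failure | Response |
| No | Yes | Failure | Failure |
| No | No | Failure | Failure |

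Only the second row is misclassified, and it moves a failure to a response. An omitted entry can therefore raise the rate but not lower it. The last column is an inference. The treatment is evaluable because pain data exist, no recorded use triggers the failure rule, and no other rule applies.

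**Step 2. Is there a second source?** Section 7.1 names patient-reported collection in the app as the means of data capture. The final visit in 5.2 mentions device return and questionnaires whose content is not given. The per-protocol set in 6.3 uses a rescue criterion, but no separate source for it is described, so it offers no independent check.

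**Step 3. Size.** The documents state no rescue rate, logging rate or response rate, so there is no plan figure to reproduce. Every rate below is an assumption.

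Upward bias = r × u × q, where r is the share taking rescue before 2 hours, u the share of that use not entered, and q the share of those participants with a lower grade at 2 hours.

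- Central illustration: 0.30 × 1/3 × 0.50 = 0.050, or 5.0 percentage points.
- Low end: 0.20 × 0.20 × 0.40 = 0.016, or 1.6 points.
- High end: 0.40 × 0.50 × 0.60 = 0.120, or 12.0 points.
- A different set of ranges (r 10–30%, u 25–100%, q 40–60%) runs from 0.10 × 0.25 × 0.40 = 1.0 point to 0.30 × 1.00 × 0.60 = 18.0 points.

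**Step 4. Against the planned precision.** Section 6.4.4 plans exact 95% intervals. Take 100 analysed participants, the most the protocol allows.

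- 50 apparent responders: 50.0% (39.8% to 60.2%). The half-width is about 10.2 points, so a 5.0-point bias is about half of it.
- 60 apparent responders: 60.0% (49.7% to 69.7%). If 20% of them (12) had unrecorded rescue, the rate by definition is 48/100 = 48.0%, below the reported lower limit. If 10% (6) had, it is 54.0%, inside the interval.
- With 50 apparent responders, 20% (10) gives 40.0%, just inside the interval; 30% (15) gives 35.0%, outside it.

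**The case against.** The strongest reply is that the documents are silent rather than wrong, and much of it stands.

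- A reader might infer that the plan prescribes treating a missing entry as no rescue. No sentence says so; it follows only from the rules taken together.
- A reader might infer that the app has no rescue question. The list of 2-hour entries in 5.2 cannot show that, because it also omits functional disability and vomiting, both of which are analysed. Section 3.3 describes the diary by example only, and its screens are not shown in the text available here. The final questionnaires are unspecified, and the baseline ones do cover abortive medication.
- Logging is instructed, with time and drug, so it is not left to goodwill. Under such an instruction no entry is in effect a report of no use, and the risk is under-reporting rather than a formal imputation of missing data.
- The Synopsis admits to treatment only participants with at least 22 diary entries in the 28-day run-in. That favours people who use the app reliably and argues against high unlogged shares.
- The instruction to avoid rescue may reduce early use as well as its reporting; the documents do not show which. A dose taken after 2 hours but entered with an earlier time would bias the rate downward, so the one-way direction applies to omitted entries, not to every recording error.
- There is no performance goal or hypothesis test, so no pre-specified decision would change.

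What remains is that the stated method cannot separate no use from unrecorded use, and that 6.4.4 has no rule for unknown status.

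**Conclusion.** The point holds as a gap in capture and analysis rules for one component of the primary endpoint. As written, a relieved test treatment with no medication entry would count as a response whether or not a drug was taken. Omitted entries would raise the primary rate and the functional-disability and consistency rates that share the condition.

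The size is unknown. A few percentage points is a plausible illustration, but it rests wholly on assumed rates, and the run-in requirement may make it smaller. A reader might go further and conclude that the reported rate will be inflated by a known amount; the documents do not support that. If the app or the final questionnaires already ask the question, the sponsor need only say so and add the analysis rule. This is an inexpensive improvement, not a flaw that invalidates the design.

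**What to change.** **Section 5.2.** Make a yes/no answer on rescue medication a required part of the 2-hour entry for every treatment, with time and drug if yes. Word it to cover medication taken before the treatment as well as after its start, so that the same item serves the per-protocol criterion in 6.3.

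**Section 6.4.4.** State that rescue status is known only when that item is answered. Report the primary rate together with a sensitivity analysis that counts unknown rescue status as non-response, and give the number of test treatments with unknown status.

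**Cost.** One app item and a short addition to the analysis text, a few seconds per session, and possibly a slightly lower reported rate. The change concerns recording and analysis only; it does not touch the clinical rule on rescue use.
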